N is the number of subjects assessed for signs/symptoms at the particular visit.

'n' represents the number of subjects who reported each sign or symptom at the Visit(s) indicated.

The same subject may be counted at all visits;

*Only some subjects have data at Visit 3 due to the protocol amendment.

1 The denominator of the percentage is the number of subjects for each visit.

2 The denominator of the percentage is the number of males for each visit.

3 The denominator of the percentage is the number of females for each visit.

Table 32: Summary of Baseline Categorical Sexual History—ITT population

Sexual History Interview Question	Value	All Subjects (N=X)	
		n	%
1. What is your gender identity?	Man	x	xx
	Woman	x	xx
	Trans male/Trans man	x	xx
	Trans female/Trans woman	x	xx
	Genderqueer/Gender non-conforming	x	xx
	Multiple	x	xx
	Other	x	xx
	Refused to Answer	x	xx
2. What is your sexual orientation?	Heterosexual/Straight	x	xx
	Homosexual/gay/lesbian	x	xx
	Bisexual	x	xx
	Other	x	xx
	Refused to Answer	x	xx
3. Do you have sex with men, women, transgender men, transgender women, or multiple genders?	Men	x	xx
	Women	x	xx
	Trans male/Trans man	x	xx
	Trans female/Trans woman	x	xx
	Multiple	x	xx
	Refused to Answer	x	xx
4. Have you had sex (vaginal, anal, or oral) in the past 30 days?	Yes	x	xx
	No	x	xx
	Refuse to answer	x	xx

N=Number of all enrolled subjects

Table 33: Summary of Follow-up Categorical Sexual History—All Enrolled Subjects

Sexual History Interview Question	Value	Visit 2 (N=X)		Unscheduled Visit (N=X)		All Subjects (N=X)	
		n	%	n	%	n	%
1. Have you had sex (vaginal, anal, or oral) since the last visit?	Yes	x	xx	x	xx	x	xx
	No	x	xx	x	xx	x	xx
	Refuse to answer	x	xx	x	xx	x	xx
2. Have you had vaginal intercourse since the last visit?	Yes	x	xx	x	xx	x	xx
	No	x	xx	x	xx	x	xx
	Refuse to answer	x	xx	x	xx	x	xx
If Yes for question 2, did you use a condom with vaginal intercourse ¹	No	x	xx	x	xx	x	xx
	Always	x	xx	x	xx	x	xx
	Sometimes	x	xx	x	xx	x	xx
	Unknown	x	xx	x	xx	x	xx
	Refuse to answer	x	xx	x	xx	x	xx
3. Have you given oral intercourse since the last visit?	Yes	x	xx	x	xx	x	xx
	No	x	xx	x	xx	x	xx
	Refuse to answer	x	xx	x	xx	x	xx
If Yes for question 3, did you use a condom or barrier with oral intercourse? ²	No	x	xx	x	xx	x	xx
	Always	x	xx	x	xx	x	xx
	Sometimes	x	xx	x	xx	x	xx
	Unknown	x	xx	x	xx	x	xx
	Refuse to answer	x	xx	x	xx	x	xx
4. Have you received oral intercourse since the last visit?	Yes	x	xx	x	xx	x	xx
	No	x	xx	x	xx	x	xx
	Refuse to answer	x	xx	x	xx	x	xx
If Yes for question 4, did you use a condom or barrier with oral intercourse? ³	No	x	xx	x	xx	x	xx
	Always	x	xx	x	xx	x	xx
	Sometimes	x	xx	x	xx	x	xx
	Unknown	x	xx	x	xx	x	xx
	Refuse to answer	x	xx	x	xx	x	xx
5. Have you had receptive 'bottom' anal intercourse since the last visit?	Yes	x	xx	x	xx	x	xx
	No	x	xx	x	xx	x	xx
	Refuse to answer	x	xx	x	xx	x	xx

Table 33: Summary of Follow-up Categorical Sexual History — All Enrolled Subjects (Continued)

Sexual History Interview Question	Value	Visit 2 (N=X)		Unscheduled Visit (N=X)		All Subjects (N=X)	
		n	%	n	%	n	%
If Yes for question 5, did you use a condom with receptive anal intercourse? ⁴	No	x	xx	x	xx	x	xx
	Always	x	xx	x	xx	x	xx
	Sometimes	x	xx	x	xx	x	xx
	Unknown	x	xx	x	xx	x	xx
	Refuse to answer	x	xx	x	xx	x	xx
6. Have you had insertive ‘top’ anal intercourse since the last visit? (Males only) ⁵	No	x	xx	x	xx	x	xx
	Yes	x	xx	x	xx	x	xx
	Refused to answer	x	xx	x	xx	x	xx
	N/A (if female)	x	xx	x	xx	x	xx
If Yes for question 6, did you use a condom with insertive anal intercourse? ⁶	No	x	xx	x	xx	x	xx
	Always	x	xx	x	xx	x	xx
	Sometimes	x	xx	x	xx	x	xx
	Unknown	x	xx	x	xx	x	xx
	Refuse to answer	x	xx	x	xx	x	xx

N=Number of enrolled subjects at the specific visit.

¹ The denominator of the percentage for this question is the number of subjects answered “yes” for question 2 at each visit.² The denominator of the percentage for this question is the number of subjects answered “yes” for question 3 at each visit.³ The denominator of the percentage for this question is the number of subjects answered “yes” for question 4 at each visit.⁴ The denominator of the percentage for this question is the number of subjects answered “yes” for question 5 at each visit.⁵ The denominator of the percentage for this question is the number of male subjects at each visit.⁶ The denominator of the percentage for this question is the number of male subjects answered “yes” for question 6 at each visit.

Table 34: Side Effects of Fluoroquinolone Use

Summary	Visit 1 (N = x)		Visit 2 (N = x)		Visit 3* (N = x)	
	n	%	n	%	n	%
Tendon Pain	x	xx	x	xx	x	xx
Joint Pain	x	xx	x	xx	x	xx
Muscle Pain	x	xx	x	xx	x	xx
Tingling or Pricking Sensation	x	xx	x	xx	x	xx
Confusion	x	xx	x	xx	x	xx
Hallucinations	x	xx	x	xx	x	xx

N is the number of subjects whose assessments were collected at the particular visit.

'n' represents the number of subjects who reported each sign or symptom at the Visit(s) indicated.

The denominator of the percentage is the number of subjects whose assessments were collected at the particular visit.

The same subject may be counted at all visits.

*Only some subjects have data at Visit 3 due to the protocol amendment.

Table 35: Number and Percentage of Subjects with Prior and Concomitant Medications Contraindicated with Ciprofloxacin or Systemic Antibiotics by WHO Drug Classification—All Enrolled Subjects

WHO Drug Code Level 1, Anatomic Group	WHO Drug Code Level 2, Therapeutic Subgroup	All Subjects (N=X)	
		n	%
Any Level 1 Codes	Any Level 2 Codes	x	x
[ATC Level 1 - 1]	Any	x	x
	[ATC 2 - 1]	x	x
	[ATC 2 - 2]	x	x
	[ATC 2 - 3]	x	x
[ATC Level 1 – 2]	Any	x	x
	[ATC 2 - 1]	x	x
	[ATC 2 - 2]	x	x
	[ATC 2 - 3]	x	x

N= Number of all enrolled subjects

n=Number of subjects reporting taking at least one medication in the specific WHO Drug Class.

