6. GENERAL STATISTICAL CONSIDERATIONS

6.1. General Principles

Tabulations will be used extensively to summarize the data. All continuous variables will be summarized using some or all of the following descriptive statistics: n (samples size), mean, standard deviation, median, maximum, and minimum. The frequency and percentages (based on the sample size) of observed levels will be reported for all categorical measures. Modified Jeffreys confidence intervals (CIs) for binomial proportions will be computed for efficacy variables [2]. A 5% one-sided significance level will be used; i.e. one-sided 95% confidence intervals will be generated. In general, all data will be listed, sorted by site and subject, and when appropriate by visit number within subject. All summary tables will be annotated with the total population size relevant to that table, including any missing observations.

Note that in the data listing, Subject ID is the unique subject identifier, not the Study ID used on study, and dates will not be included, only Study Day. Study Day 1 will be the day of the dose of treatment.

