6.3.2.2. Microbiological Intent-to-Treat (micro-ITT) Population

For the primary analysis, the micro-ITT population includes all enrolled subjects who have wild type *gyrA* serine 91 *N. gonorrhoeae* isolated from the rectum or urogenital site on Day 1 culture. Subjects with infections at multiple anatomic sites are included as long as one of the infected sites is the rectum or urogenital site. Subjects with infections at multiple anatomic sites must be wild-type at each culture-positive site to be included in the primary analysis.

Subjects with non-evaluable outcome status will be included in the micro-ITT population and classified as microbiological failures. Subjects who discontinued early from the study with lack of treatment effect being the documented reason for discontinuation will be included as microbiological failures. Subjects who vomited within 1 hour of administration will be included as microbiological failures.

For the analysis of secondary objective 1, subjects need to have wild type *gyrA* serine 91 *N. gonorrhoeae* isolated on Day 1 culture at the particular anatomical site being assessed. The results at the other anatomical sites will not be considered when determining a subject's eligibility into each of the site-specific populations.

There will be four micro-ITT populations identified:

- Primary micro-ITT population
- Rectal micro-ITT population
- Urogenital micro-ITT population
- Pharyngeal micro-ITT population

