8.2. Secondary Efficacy Analyses

The analysis of the first secondary endpoint will proceed using the same methods as the primary efficacy analysis using the anatomical site-specific definition of microbiological outcome status (see Section 3.3.2). Summaries of the cure rate and associated confidence interval will be generated for each individual anatomical site and analysis population (Table 11).

For the analysis of the second secondary endpoint, the sensitivity and positive predictive value of the *gyrA* assay will be estimated as described in Section 3.3.3. This analysis will be performed by anatomic sites in the ITT analysis population. See Table 12.

The summaries of *N. gonorrhoeae* culture results, NAAT testing results and *gyrA* assay results will be presented by each anatomical site and visit (Table 13, Table 14, and Table 15). Listing 5 and Listing 6 provide a complete listing of individual microbiological results.

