8.3. Exploratory Efficacy Analyses

The proportion of subjects infected with *gyrA* serine 91 genotype *N. gonorrhoeae* with microbiological cure at Visit 2 will be summarized by demographic (sex, age, race, ethnicity) and clinical characteristics (symptomatic status and re-exposure status at follow up by anatomic sites). Age will be broken into two categories based on the median age: Age < median and Age ≥ median for each analysis population. The microbiological cure rate will be calculated separately for each category. See [Table 21](#) and [Table 26](#). The analyses by demographics will be repeated on the infection level, as well (see [Table 22](#), [Table 23](#), [Table 24](#), and [Table 25](#)).

The genomic analyses of identification and characterization of non-*gyrA* gene-dependent mechanisms of ciprofloxacin resistance by genotyping and whole genome sequencing of nucleic acid isolated from uncured subjects at Visit 2 will be described in a separate statistical analysis plan.

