Table 8: Microbiological Cure Rate by Analysis Population

Analysis Population	Statistic	All Subjects
Intent-to-Treat (ITT) Population	Number of Subjects with Microbiological Cure, n	x
	Number of Subjects, N	x
	Microbiological Cure Rate, %	xx.x
	95% CI, %	xx.x, 100
Microbiological Intent-to-Treat (micro-ITT) Population	Number of Subjects with Microbiological Cure, n	x
	Number of Subjects, N	x
	Microbiological Cure Rate, %	xx.x
	95% CI, %	xx.x, 100
Per Protocol (PP) Population	Number of Subjects with Microbiological Cure, n	x
	Number of Subjects, N	x
	Microbiological Cure Rate, %	xx.x
	95% CI, %	xx.x, 100

Table 9: Microbiological Cure Rate by Analysis Population and Alternate Confidence Interval

Analysis Population	Statistic	All Subjects
Intent-to-Treat (ITT) Population	Number of Subjects with Microbiological Cure, n	x
	Number of Subjects, N	x
	Microbiological Cure Rate, %	xx.x
	95% Jeffreys CI*, %	xx.x, 100
	95% Wilson CI, %	xx.x, 100
	95% Agresti-Coull CI, %	xx.x, 100
	95% Blaker CI, %	xx.x, 100
Microbiological Intent-to-Treat (micro-ITT) Population	Number of Subjects with Microbiological Cure, n	x
	Number of Subjects, N	x
	Microbiological Cure Rate, %	xx.x
	95% Jeffreys CI, %	xx.x, 100
	95% Wilson CI, %	xx.x, 100
	95% Agresti-Coull CI, %	xx.x, 100
	95% Blaker CI, %	xx.x, 100
Per-Protocol (PP) Population	Number of Subjects with Microbiological Cure, n	x
	Number of Subjects, N	x
	Microbiological Cure Rate, %	xx.x
	95% Jeffreys CI, %	xx.x, 100
	95% Wilson CI, %	xx.x, 100
	95% Agresti-Coull CI, %	xx.x, 100
	95% Blaker CI, %	xx.x, 100

*95% Modified Jeffrey CI is the primary confidence interval.

Table 10: Microbiological Cure Rate by Analysis Population (Alternate Definitions)

Analysis Population	Statistic	All Subjects
Modified micro-ITT Population	Number of Subjects with Microbiological Cure. n	x
	Number of Subjects, N	x
	Microbiological Cure Rate, %	xx.x
	95% Jeffreys CI*, %	xx.x, 100
Modified PP Population	Number of Subjects with Microbiological Cure, n	x
	Number of Subjects. N	x
	Microbiological Cure Rate, %	xx.x
	95% Jeffreys CI, %	xx.x, 100
Alternate PP Population	Number of Subjects with Microbiological Cure, n	x
	Number of Subjects. N	x
	Microbiological Cure Rate, %	xx.x
	95% Jeffreys CI, %	xx.x, 100

Table 11: Microbiological Cure Rate by Anatomical Site and Analysis Population

Analysis Population	Statistic	Urethral/Cervical	Rectal	Pharyngeal	All Anatomical Sites

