Intent-to-Treat (ITT) Population	Number of Infections with Microbiological Cures, n	x	x	x	x
	Number of Infections, N	x	x	x	x
	Microbiological Cure Rate, %	xx.x	xx.x	xx.x	xx.x
	95% CI, %	xx.x, 100	xx.x, 100	xx.x, 100	xx.x, 100
Microbiological Intent-to-Treat (micro-ITT) Population	Number of Infections with Microbiological Cure, n	x	x	x	x
	Number of Infections, N	x	x	x	x
	Microbiological Cure Rate, %	xx.x	xx.x	xx.x	xx.x
	95% CI, %	xx.x, 100	xx.x, 100	xx.x, 100	xx.x, 100
Per-Protocol (PP) Population	Number of Infections with Microbiological Cure, n	x	x	x	x
	Number of Infections, N	x	x	x	x
	Microbiological Cure Rate, %	xx.x	xx.x	xx.x	xx.x
	95% CI, %	xx.x, 100	xx.x, 100	xx.x, 100	xx.x, 100

Implementation Notes: The ITT Population, Micro-ITT Population and PP Population will be based on the anatomical site.

Table 12: Summary of *gyrA* Assay Results and Culture-Based Antimicrobial Susceptibility Testing at Visit 1—ITT population

	Anatomic Site		Culture-Based Antimicrobial Susceptibility Testing					
			Susceptible		Not Susceptible		Total	
			n	%	n	%	n	%
gyrA Assay	All Sites	Wild Type gyrA detected	xx	xx	xx	xx	xx	xx
		Mutant gyrA detected	xx	xx	xx	xx	xx	xx
		Total	xx	xx	xx	xx	xx	100
	Urethral	Wild Type gyrA detected	xx	xx	xx	xx	xx	xx
		Mutant gyrA detected	xx	xx	xx	xx	xx	xx
		Total	xx	xx	xx	xx	xx	100
	Cervical	Wild Type gyrA detected	xx	xx	xx	xx	xx	xx
		Mutant gyrA detected	xx	xx	xx	xx	xx	xx
		Total	xx	xx	xx	xx	xx	100
	Rectal	Wild Type gyrA detected	xx	xx	xx	xx	xx	xx
		Mutant gyrA detected	xx	xx	xx	xx	xx	xx
		Total	xx	xx	xx	xx	xx	100
	Pharyngeal	Wild Type gyrA detected	xx	xx	xx	xx	xx	xx
		Mutant gyrA detected	xx	xx	xx	xx	xx	xx
		Total	xx	xx	xx	xx	xx	100

The denominator for percentages is based on the number of instances in which swabs taken from a subject at Visit 1 resulted in a determinate *gyrA* Assay result and a determinate culture-based antimicrobial susceptibility test result. If either *gyrA* Assay result or culture-based antimicrobial susceptibility test result is indeterminate or missing, both results will be excluded. Susceptible is defined as an MIC of < 1 ug/ml as reported by the antimicrobial susceptibility testing.

Implementation Notes: The ITT Population will be based on the anatomical site.

Table 13: Culture Results by Time Point and Anatomical Sites

Time Point	Result	Urethral (N=X)		Cervical (N=X)		Rectal (N=X)		Pharyngeal (N=X)	
		n	%	n	%	n	%	n	%

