Implementation Notes: The analysis populations will be based on the anatomical site.

Table 26: Microbiological Cure Rate by Clinical Characteristics—Micro-ITT Population

Statistics	Cervical		Urethral		Rectal		Pharyngeal		All Anatomical Sites	
	Symptomatic Status		Symptomatic Status		Symptomatic Status		Symptomatic Status		Symptomatic Status	
	Symptomatic	Asymptomatic	Symptomatic	Asymptomatic	Symptomatic	Asymptomatic	Symptomatic	Asymptomatic	Symptomatic	Asymptomatic
Number of Infections with Microbiological Cure, n	x	x	x	x	x	x	x	x	x	x
Number of Infections, N	x	x	x	x	x	x	x	x	x	x
Microbiological Cure Rate	xx.x	xx.x	xx.x	xx.x	xx.x	xx.x	xx.x	xx.x	xx.x	xx.x
Microbiological Cure Rate 95% CI, %	xx.x, 100	xx.x, 100	xx.x, 100	xx.x, 100	xx.x, 100	xx.x, 100	xx.x, 100	xx.x, 100	xx.x, 100	xx.x, 100
	Re-exposure at Follow up		Re-exposure at Follow up		Re-exposure at Follow up		Re-exposure at Follow up		Re-exposure at Follow up	
	Sex with Protection	Sex without Protection	Sex without Protection	Sex without Protection	Sex without Protection	Sex without Protection	Sex without Protection	Sex without Protection	Sex without Protection	Sex without Protection
Number of Infections with Microbiological Cure, n	x	x	x	x	x	x	x	x	x	x
Number of Infections, N	x	x	x	x	x	x	x	x	x	x
Microbiological Cure Rate, %	xx.x	xx.x	xx.x	xx.x	xx.x	xx.x	xx.x	xx.x	xx.x	xx.x
Microbiological Cure Rate 95% CI, %	xx.x, 100	xx.x, 100	xx.x, 100	xx.x, 100	xx.x, 100	xx.x, 100	xx.x, 100	xx.x, 100	xx.x, 100	xx.x, 100

Implementation Notes: The Micro-ITT Population will be based on the anatomical site.

Table 27: Summary of Categorical Demographic and Baseline Characteristics by Site—All Enrolled Subjects

Variable	Characteristic	AIDS Healthcare Foundation (N=X)		Los Angeles LGBT Center (N=X)		San Francisco Department of Public Health (N=X)		Philadelphia Department of Public Health (N=X)		University of Mississippi Medical Center (N=X)		Louisiana State University (N=X)		University of California, San Diego Antiviral Research Center (N=X)		Whitman-Walker Health (N=X)		All Subjects (N=X)	
		n	%	n	%	n	%	n	%	n	%	n	%	n	%	n	%	n	%
Sex	Male	x	xx	x	xx	x	xx	x	xx	x	xx	x	xx	x	xx	x	xx	x	xx
Ethnicity	Female	x	xx	x	xx	x	xx	x	xx	x	xx	x	xx	x	xx	x	xx	x	xx
	Not Hispanic or Latino	x	xx	x	xx	x	xx	x	xx	x	xx	x	xx	x	xx	x	xx	x	xx
	Hispanic or Latino	x	xx	x	xx	x	xx	x	xx	x	xx	x	xx	x	xx	x	xx	x	xx
	Not Reported	x	xx	x	xx	x	xx	x	xx	x	xx	x	xx	x	xx	x	xx	x	xx
Race	Unknown	x	xx	x	xx	x	xx	x	xx	x	xx	x	xx	x	xx	x	xx	x	xx

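### The pooled infection-level columns of SAP Tables 11, 22 and 26 use a single-binomial bound on infections clustered within subjects, so the nominal 95% level is modestly overstated

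*SAP*

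**What the plan says.** SAP 6.1 sets the general rule: "Modified Jeffreys confidence intervals (CIs) for binomial proportions will be computed for efficacy variables", and "A 5% one-sided significance level will be used; i.e. one-sided 95% confidence intervals will be generated". Three tables then pool infections across sites.

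- **Table 11.** Under SAP 8.2, "The analysis of the first secondary endpoint will proceed using the same methods as the primary efficacy analysis". The shell's numerator row in the ITT block is "Number of Infections with Microbiological Cures, n", and the denominator is counted as "Number of Infections, N" in the ITT, micro-ITT and PP blocks, with columns for urethral/cervical, rectal, pharyngeal and "All Anatomical Sites". The text of 8.2 promises intervals only for each individual site; the pooled column exists only in the shell.
- **Table 22** (all infections). It is planned in SAP 8.3: "The analyses by demographics will be repeated on the infection level". Section 8.3 names no interval method, so SAP 6.1 supplies it.
- **Table 26** (clinical characteristics, micro-ITT only). It is also planned in 8.3, is counted in infections and has a pooled column.

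Subjects can contribute more than once. SAP 6.3.2.2 states: "Subjects with infections at multiple anatomic sites are included as long as one of the infected sites is the rectum or urogenital site". SAP 6.3.2.3 says the same for PP. No cluster adjustment, robust variance or subject-level resampling appears anywhere in the SAP.

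**The concern.** The Jeffreys bound is derived for N independent trials. In a pooled column, N counts infections, and infections in one subject share a host, a single dose and one follow-up visit. If outcomes within a subject are positively correlated, the information is worth fewer than N independent observations. The lower bound is then too high, and its real coverage is below the printed 95%. The error favours the drug. Protocol 11.1 makes 95% the reference line for a recommended treatment, so readers may hold a printed pooled bound against it.

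**Working it through.** **1. The plan's own figure, to fix the method.** The lower bound is the 0.05 quantile of Beta(X+0.5, N−X+0.5), or 0.05^(1/N) if X=N. Protocol 11.4.3.1 prints the 0.95 quantile; the 0.05 quantile is used here because it matches the SAP 6.1.1 code and reproduces the stated power. At N=257 the bound reaches 95% with at least 250 cures. Exact power at 98% cure is 85.4% (stated: about 85%). At N=195 it is 80.2% (stated: 80%). Enrolment is 257/(0.75×0.90)=380.7, so 381. All agree.

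**2. Inputs that the documents do not give.** These are the share of subjects with two or three infected sites and the within-subject correlation ρ. Both are assumed, over a range. The base case is 257 subjects, 20% with two sites and 5% with three:

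- infections per subject: 0.75×1+0.20×2+0.05×3=1.30, so 257×1.30≈334 infections
- mean of m²: 0.75×1+0.20×4+0.05×9=2.00
- design effect: 1+ρ(2.00/1.30−1)=1+0.538ρ, which is 1.27 at ρ=0.5 and 1.43 at ρ=0.8

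**3. Coverage of the unadjusted one-sided 95% bound.** Simulation with 20,000 to 40,000 trials per setting; ranges show repeated runs.

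| ρ | true cure 95% | true cure 98% |
|---|---|---|
| 0 | 94.7–94.9% | 96.2% |
| 0.3 | 93.4% | 95.3% |
| 0.5 | 92.2–92.6% | 94.4–94.5% |
| 0.8 | 90.8–91.1% | 93.2–93.7% |

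Other mixes at 95% cure: with 10% two-site subjects, coverage is 94.2%, 93.5% and 92.7% at ρ=0.3, 0.6 and 1. With 30% two-site and 5% three-site subjects it is 93.1%, 91.9% and 90.0%.

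**4. Shift in the bound.** Replace N=334 by 334/design effect and keep the observed rate. At 98% the bound moves from 96.42% to 96.17% (ρ=0.5) or 96.02% (ρ=0.8). At 95% it moves from 92.74% to 92.42% or 92.23%. The overstatement is therefore about 0.2 to 0.5 points. A borderline example: 10 failures in 334 give an unadjusted bound of 95.16%; with design effect 1.27 it is 94.88%.

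**5. Correlation that the rules create.** SAP 6.3.2.1, 6.3.2.2 and 6.5 count a non-evaluable subject, and 6.3.2.1 and 6.3.2.2 a subject who vomits within one hour, as a failure. Let a share q of subjects miss Visit 2 (assumed) and let sites otherwise be independent at 98%. Then p=(1−q)×0.98 and ρ=[(1−q)×0.98²−p²]/[p(1−p)].

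- q=5%: p=0.931, ρ=(0.9124−0.8668)/0.0642=0.71
- q=10%: p=0.882, ρ=(0.8644−0.7779)/0.1041=0.83

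Take 257/0.90≈286 subjects and q=10%. Coverage is then 93.7% with 10% two-site subjects, 91.9% with 20% two-site and 2% three-site, and 90.7% with 30% and 5%. With one infection per subject it is already 93.8%, because the counts are discrete, so only the fall below 93.8% is due to clustering.

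**The case against.** The strongest reply is that nothing planned depends on these columns. SAP 8.2 and Protocol 11.4.3.2 confine the interval, and the Protocol its hypothesis test, to each individual site. The question across all sites is answered per subject in Tables 8 to 10, where a subject who stays positive at any infected site fails. Tables 22 and 26 are exploratory, and SAP 6.4 already says that the study is not powered for subgroups. This stands, and it limits the point to the labelling of the pooled intervals.

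It is also fair that the size rests on assumed inputs. At the plan's own 98% cure rate, coverage stays near nominal up to a correlation of about 0.5. In PP, where non-evaluable subjects are excluded, the documents give no evidence on correlation. Table 22 has only a title and borrows the format of Table 21, which counts subjects; its unit comes from SAP 8.3.

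A reader might infer that the trial could wrongly claim to clear 95%. In the base case at a true rate of 95%, the chance that the pooled bound reaches 95% does rise from 5.1% to 7.4% (ρ=0.5) or 9.0% (ρ=0.8). But no section tests that bound, so this is not an inflated type I error of any planned test. A reader might also infer that SAP 8.2 prescribes the method for all three tables; it governs only Table 11.

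What remains is that a column headed 95% CI should have about that coverage, and in micro-ITT and ITT the SAP's own rules work against it.

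**Conclusion.** The point holds for the pooled infection-level columns of Tables 11, 22 and 26 only. The direction of the error is settled by the failure rules in micro-ITT and ITT, and is plausible but unproven in PP. The size is modest: about 91% to 93% coverage at 95% cure, about 93% to 94.5% at 98%, and a bound about 0.2 to 0.5 points too high. These figures assume 257 subjects, 334 infections and correlation 0.5 to 0.8. They illustrate a full pooled column such as that of Table 11; the smaller subgroup cells of Tables 22 and 26 were not computed. The primary analysis, its power and the single-site columns (at most one infection per subject) are not affected.

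**What to change.** Choose one of two changes, stated in SAP 8.2 and 8.3.

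1. **Adjust the pooled bound.** Take the subject as the cluster. Estimate the design effect as the cluster-robust variance of the pooled rate divided by its binomial variance, and do not let it fall below 1. Apply the modified Jeffreys formula with effective sample size = infections / design effect. When no infection fails, the design effect cannot be estimated; use 0.05^(1/number of subjects). For 257 subjects this gives 98.8%, against 99.1% from 334 infections. In simulation at 95% cure this restores coverage to about 94% to 95%. It recovers less at 98%, where failures are few and the design effect is poorly estimated.
2. **Drop the pooled interval**, so that the Table 11 shell matches the text of SAP 8.2, and give the pooled counts and rate only.

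In either case, print the number of subjects beside the number of infections. Leave the single-site columns as they are. Do not use a percentile bootstrap of subjects: in the base case it covered only about 87% to 90% at 98% cure and 91% to 93% at 95%, and with no failures it collapses to 100%.

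The cost is a sentence or two in the SAP, a few lines of code and slightly lower pooled bounds. No new data and no change in sample size are needed.
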